1.2 Secondary Objectives

- 1.2.1 To estimate the degree to which a [¹⁴C]oxaliplatin microdose predicts the observed pharmacokinetics of standard dose oxaliplatin
- 1.2.2 To validate that intrapatient variation of exposure to a [¹⁴C]oxaliplatin microdose is less than 5%
- 1.2.3 To detect the levels of oxaliplatin-DNA adducts induced by oxaliplatin microdosing in peripheral blood mononuclear cells (PBMC), and correlate the results with patient response and progression free survival on oxaliplatin-based chemotherapy
- 1.2.4 To develop preliminary safety data of [¹⁴C]oxaliplatin microdosing for future studies

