2.3.3 Summary of Resistance to Platinum-based Chemotherapy

Owing to the complexity of the above outlined platinum-based drug resistance mechanisms, scoring mutations or gene expression changes in a few individual pathways is likely to have limited impact on developing biomarker tests for predicting

efficacy. The microdosing approach of this feasibility study provides a strategy for obtaining a comprehensive measurement of major resistance factors at play in an individual tumor, since the phenotypic in vivo capacity for Pt-DNA adduct formation and repair can be directly measured in the patient prior to initiation of platinum-based chemotherapy.

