2.6 Assessment of Microdose-induced Oxaliplatin-DNA damage

Several studies have confirmed that the levels of drug-DNA adducts directly correlate with the outcomes of platinum-based chemotherapy, particularly in peripheral blood mononuclear cells (PBMC). After Pt-based chemotherapy, DNA adducts can be detected in multiple tissues [10, 71, 72]. The concentration of Pt-DNA adducts correlates to the drug concentration and incubation time in cell culture [10]. Decreased Pt-DNA adducts are associated with resistance to Pt chemotherapy in cell lines [73]. The levels of DNA adducts, as detected by immunohistochemical staining, correlated with response to Pt chemotherapy [71, 72]. Those patients with low drug-DNA adducts or increased repair of drug-DNA adducts had worse outcomes [74]. Oxaliplatin-DNA adducts have been measured by Pieck et al [75] in peripheral blood lymphocytes from 37 patients with a variety of malignancies. In patients showing tumor response, adduct levels after 24 and 48 h were significantly higher than in nonresponders, indicating that drug-DNA adduct levels in surrogate tissues may serve as biomarkers of response. However, the commonly used drug-DNA adduct detection methods such as atomic absorption spectroscopy, Southern blot, or immunological detection with antibodies, are not sufficiently sensitive for detection of drug-DNA adducts induced by microdose concentrations of platinum drugs. Cell lines and patients need to be exposed to chemotherapeutic doses (high, toxic concentrations) for a sufficient number of drug-DNA adducts to be created for the common adduct detection methods above to be informative [76]. Therefore, these traditional approaches can ONLY identify chemoresistance in patients AFTER full-dose chemotherapy.

In this study, we will adopt the highly sensitive technology of AMS for detection of microdose-induced platinum-DNA adducts. We have shown that AMS is about 1000 times

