6 STUDY DESIGN AND TREATMENT PLAN

6.1 Study Design

This is a prospective feasibility study of a [¹⁴C]oxaliplatin microdose assay to predict exposure and sensitivity to oxaliplatin as part of standard-of-care FOLFOX chemotherapy. Consenting patients who will be receiving FOLFOX as their treatment for cancer will be enrolled. Patients will receive two [¹⁴C]oxaliplatin microdose infusions over the course of the study. The first part of the study is a Phase 0 [¹⁴C]oxaliplatin microdose infusion occurring over 2 hours and followed by serial blood draws over a 24 hour period for microdose pharmacokinetic and pharmacodynamic analysis (on surrogate peripheral blood mononuclear cells). Between 2 days and 4 weeks after the administration of this phase 0 microdose, patients will begin FOLFOX therapy according to usual care. The initial treatment oxaliplatin dose will be diluted with the same amount of [¹⁴C]oxaliplatin microdose as previously administered. Repeat blood draws for pharmacokinetic assessment of both the microdose and therapeutic dose along with pharmacodynamic analysis on PBMCs will be performed over 46-48 hours (this last draw is timed for the disconnect visit of the 5-FU infusion).

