6.3.3 Sample Collection Schedule

Blood will be collected for pharmacokinetic and pharmacodynamic analysis according to the schedule in **Table 2**. See section 10.1.1 for sample processing.

Table 2. Time Points of Blood Collection for PK Assessment after Phase 0 Microdose

Sample Number	Scheduled time points relative to ^{14}C Oxaliplatin administration		
	Day	Scheduled time	Description
1	1	0-5 min predose	Pre-dose
2	1	30 minutes (± 5 minutes)	Post-dose
3	1	1 hr (± 10 minutes)	Post-dose
4	1	1 hr 45 min (± 10 minutes)	Post-dose
5	1	2 hr (± 10 minutes)	Post-dose
6	1	2 hr 15 min (± 10 minutes)	Post-dose
7	1	3 hr (± 10 minutes)	Post-dose
8	1	4 hr (± 60 minutes)	Post-dose
9	1	24 hr (± 60 minutes)	Post-dose

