11.2.2 Secondary Analyses

Given the small number of patients included in this pilot study, all secondary analyses will be considered hypothesis generating for the design of future confirmatory study.

11.2.2.1 For secondary endpoint 8.2.2.1, we will correlate PK parameters from microdosing with parameters from therapeutic doses of oxaliplatin. All parameters will be normalized for dose. We will present descriptive summaries (scatterplots, tables, mean, SD,

correlation coefficient) of the relationship between the two sets of parameters.

11.2.2.2 For secondary endpoint 8.2.2.2, we will correlate PK parameters from phase 0 microdosing with parameters from FOLFOX-integrated microdosing of oxaliplatin. We will present descriptive summaries (scatterplots, tables, mean, SD, correlation coefficient) of the relationship between the two sets of parameters.

11.2.2.3 For secondary endpoint 8.2.2.3 and 8.2.2.4, we will characterize the repair of DNA adducts in PBMC, using descriptive statistics (graphical summaries, mean, SD, box plots). Response rate and duration of disease control (DDC) will be measured according to RECIST 1.1 (**Appendix C**). The DDC is equivalent to progression free survival if an intermittent oxaliplatin strategy is not employed. Progression free survival will be calculated from the date of enrollment to the date of first objective evidence of radiographic progression (soft tissue or bone lesion) or date of death due to any cause, whichever occurs first. If an intermittent oxaliplatin strategy is chosen, we will define DDC as the addition of the initial PFS and the PFS of the reintroduction, except in case of progression at the first evaluation after FOLFOX reintroduction. Radiological assessment by the treating Investigator will be the primary report in this analysis. We hypothesize that higher levels of DNA repair will be associated with non-response and shorter duration of disease control.

11.2.2.4 For secondary endpoint 8.2.2.5, we will assess toxicity to both micordoses of [¹⁴C]oxaliplatin. Toxicities potentially related to [¹⁴C]oxaliplatin will be assessed from initiation of the study to at least 14 days after the administration of the FOLFOX-integrated microdose or until full recover of toxicity (whichever is longer). Safety will be assessed through summaries of adverse events and laboratory evaluations. Descriptive statistics will be used rather than inferential statistics.

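### Section 11.2.2.3 analyses DNA repair where the endpoints call for adduct levels, and with one phase 0 draw after 4 h the change in adducts is net of formation and repair

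*Combined protocol and SAP*

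**What the plan says.** Secondary objective 1.2.3 is written in terms of levels: "To detect the levels of oxaliplatin-DNA adducts induced by oxaliplatin microdosing in peripheral blood mononuclear cells", to be correlated with response and progression-free survival. Endpoints 8.2.2.3 and 8.2.2.4 are associations of adducts with RECIST response and with duration of disease control. Section 10.3 says adduct frequencies will be reported and refers to section 11.2 for how levels are compared with response.

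Section 11.2.2.3, written for those two endpoints, plans descriptive statistics on repair and adds: "We hypothesize that higher levels of DNA repair will be associated with non-response and shorter duration of disease control". It names no repair measure, interval, model or microdose.

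The legend to Figure 1 (section 2.1) takes the repair rate from the loss of 14C from genomic DNA. Section 2.3.3 claims that "the phenotypic in vivo capacity for Pt-DNA adduct formation and repair can be directly measured in the patient prior to initiation of platinum-based chemotherapy".

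On sampling, section 6.1 describes the phase 0 infusion as "followed by serial blood draws over a 24 hour period for microdose pharmacokinetic and pharmacodynamic analysis". In Table 2 the draws after the pre-dose sample are at 0.5, 1, 1.75, 2, 2.25, 3, 4 and 24 h. For cycle 1, section 6.1 says "pharmacodynamic analysis on PBMCs will be performed over 46-48 hours", and Table 3 adds a 48 h draw. Table 3 also has a pre-dose draw. It falls 2 days to 4 weeks after phase 0, before any therapeutic oxaliplatin.

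**The concern.** Two things do not fit together. First, objective, endpoints and laboratory section all ask for adduct levels against outcome, while the one paragraph that should say how this is done discusses repair. An analyst following 11.2.2.3 has no defined variable for the endpoint.

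Second, if repair is taken as the fall in adducts within phase 0, the available interval is 4 to 24 h, and drug is still present throughout it. A patient who clears drug slowly keeps forming adducts and looks like a slow repairer. A patient who clears fast looks like a fast repairer. This bias runs towards the stated hypothesis. Section 2.2 suggests that a short platinum half-life explains some resistance, so an exposure effect on response could be reported as a repair effect. Section 11.2.1 says the adduct data will help decide how the assay is developed, so the label matters even in a pilot.

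**Working it through.** **Step 1: the protocol's own figure.** Section 3.1.4.2 uses a 16.8 h half-life and treats drug as negligible after five half-lives: 5 × 16.8 = 84 h. This reproduces. The last phase 0 draw comes at 24/84 = 29% of that time.

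**Step 2: share of the 16.8 h phase left after the 2 h infusion**, from 2^(−(t − 2)/16.8):

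- 4 h: 2^(−2/16.8) = 0.92
- 24 h: 2^(−22/16.8) = 0.40
- 48 h: 2^(−46/16.8) = 0.15
- 84 h: 2^(−82/16.8) = 0.03

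These are shares of one phase, not of total drug. The documents do not give the relative size of the phases.

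**Step 3: what the 4-to-24 h change measures.** An illustrative model is dA/dt = kf·C(t) − kr·A, where A is the adduct level, kf the formation constant, kr the repair rate and C(t) the plasma curve after a 2 h infusion. C(t) uses the protocol's half-lives of 0.43, 16.8 and 391 h. The following are assumptions, since the documents give no values: three sets of phase coefficients, repair half-lives of 6 to 48 h, and an assay CV of 20%. Each cell below is the ratio of the 24 h to the 4 h adduct level.

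| Phase coefficients (0.43 / 16.8 / 391 h) | Share of 0–24 h exposure after 4 h | Repair 6 h | 12 h | 24 h | 48 h |
|---|---|---|---|---|---|
| 0.95 / 0.04 / 0.01 | 49% | 0.52 | 0.91 | 1.30 | 1.58 |
| 0.85 / 0.12 / 0.03 | 68% | 1.04 | 1.66 | 2.24 | 2.64 |
| 0.70 / 0.25 / 0.05 | 76% | 1.43 | 2.25 | 2.98 | 3.48 |

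In 10 of the 12 cells adducts are still higher at 24 h than at 4 h. A patient with a 6 h repair half-life and the slowest plasma profile shows a ratio of 1.43. One who repairs four times more slowly (24 h) with the fastest profile shows 1.30. The raw change ranks these two patients the wrong way round on repair. At 24 h, formation still runs at 0.74 to 2.3 times the rate of repair.

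**Step 4: could a model separate the two?** Taking plasma C(t) as known, the Fisher information at the Table 2 times gives this relative standard error for kr in one patient:

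| Repair half-life | Table 2 draws | Draws to 4 h only |
|---|---|---|
| 6 h | 20–24% | 105–133% |
| 12 h | 29–36% | 205–256% |
| 24 h | 51–64% | 406–504% |
| 48 h | 97–121% | 807–1000% |

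So kf and kr are both estimable in principle, but nearly all the information on repair comes from the single 24 h draw.

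**The case against.** The strongest reply is that this is loose wording in an exploratory section. Section 11.2.2 makes every secondary analysis hypothesis generating, and section 11.3 plans six patients. Read with 8.2.2.3, 8.2.2.4 and 10.3, adduct levels can still be taken as the outcome variable, with repair added. That stands as a limit on severity. It does not supply the missing comparison, because 10.3 defers to 11.2.

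A reader might go further than the documents allow in four ways.

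- *Repair cannot be separated from formation at all.* Step 4 shows that a joint model could do it, with weak precision. The supportable statement is that the planned descriptive analysis cannot.
- *The outcome analysis rests on repair measured before chemotherapy.* The before-chemotherapy claim is in the background (2.3.3) and covers formation as well as repair. Section 11.2.2.3 is not limited to phase 0.
- *The repair hypothesis has no stated support.* Section 2.6 does report worse outcomes with increased repair, although the bibliography title shows a melphalan study. The oxaliplatin evidence there concerns levels: in responders, "adduct levels after 24 and 48 h were significantly higher than in nonresponders".
- *There is no late sample before therapeutic drug.* The cycle 1 pre-dose draw is one. By the step 2 formula, 15% or less of the 16.8 h phase remains by then. Its timing varies, and the plan does not assign it to repair.

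Continued adduct formation is also an inference. Section 3.2.3 says no unchanged oxaliplatin is found 2 h after dosing, and section 2.2 says about half is excreted in urine within 6 h. Against that, sections 3.1.2 and 3.2.3 describe reactive platinum products that carry the labelled ring, and the 16.8 h figure is for ultrafilterable platinum. The inference is reasonable but not shown.

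Finally, the 24 h adduct level also depends on exposure. That is true, but a level reported as a level is not mislabelled, and it is what the endpoints ask for.

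**Conclusion.** The point holds as a recommended correction to a secondary, exploratory analysis. The mismatch between 11.2.2.3 and objective 1.2.3, endpoints 8.2.2.3 and 8.2.2.4 and section 10.3 is on the page and needs no assumption. The sampling limit rests on the protocol's own half-life: 92% of that phase at 4 h and 40% at the last phase 0 draw. A raw phase 0 change would therefore be net of formation and partly driven by clearance, and the plan names no method to remove that. The ratios and standard errors in steps 3 and 4 show scale only. They depend on the assumed coefficients, repair half-lives and assay CV, treat plasma 14C as the reactive species, and ignore turnover of blood cells. The primary pharmacokinetic endpoint is not affected.

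**What to change.** In 11.2.2.3:

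- Name the phase 0 adduct level at 24 h as the variable related to response and to duration of disease control. Make the cycle 1 levels at 24 h and 48 h the second comparison, stated as following the therapeutic dose.
- Report any difference between draws as net adduct change, not as a repair rate.
- Keep the repair hypothesis as exploratory. Show it beside each patient's plasma AUC or clearance and, where useful, use the cycle 1 pre-dose draw as a late point at its actual time since phase 0.

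In 2.3.3, soften the text so that it does not say repair is directly measured before chemotherapy. The statement about formation can stay.

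The cost is wording in two sections; no new sample is needed. The study gives up its claim to a direct pre-treatment measure of repair, and the 24 h level will still reflect exposure as well as repair.

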11.3 Sample Size

The number of subjects required to provide 80% probability that a 95% CI for the ratio of geometric means of full dose and micro dose PK parameters is within 2 fold (i.e., from 0.5 to 2) depends on the coefficient of variation (CV) of the ratio of the parameters, which depends on the CV of each parameter and the within-person correlation between the full dose and micro dose parameters (on a log scale). According to the Lappin et al. [77], CVs for $t_{1/2}$ were in the 0.3-0.5 range for diazepam and midazolam (which had good concordance between doses as well as adequate bioavailability). With these specifications, a sample size of 6 patients receiving both full- and micro-doses is sufficient.

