In phase I studies, the calculated exposure or area under the curve (AUC) of oxaliplatin administered at 85 mg/m² averaged 4.68 µg/mL/hr; however, there was significant inter-patient variation in AUC (SD 1.40 µg/mL/hr). The metabolism of oxaliplatin occurs in a triphasic manner. The initial ($T_{1/2\alpha}$), second ($T_{1/2\beta}$) and terminal ($T_{1/2\gamma}$) phase half-lives of oxaliplatin are reported to be 25.8 minutes, 16.8 hours and 391 hours, respectively [8, 9]. Approximately half of oxaliplatin is excreted in urine within the first 6 hours. Only a small fraction of oxaliplatin is excreted at the terminal phase. Because the formation of Pt-DNA adducts correlated to the concentration and incubation time of cells with Pt [10], and because there is a linear correlation between gross levels of platinum bound to DNA and the extent of cytotoxicity [11], it is conceivable that those patients with longer serum half-life of Pt may have more cytotoxic effects. We hypothesize that increased metabolism (short half-life) may be responsible for some cases of resistance to Pt agents. Therefore, a PK study may identify those patients with a short half-life of Pt and help design personalized therapy studies altering the dose of oxaliplatin to overcome resistance.

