2.7 Rationale for the Current Study

While oxaliplatin-based chemotherapy forms the basis of treatment for patients with various gastrointestinal cancers, methods to individualize this treatment based on expected response or observed exposure are urgently needed. For the reasons described in the preceding sections, our ***overall goal*** is to develop a ^{14}C oxaliplatin microdosing assay. The assay will simultaneously 1) individualize oxaliplatin dosing and 2) predict response (or lack thereof) to oxaliplatin-based chemotherapy in individual patients. As an intermediate step toward that goal, the primary aim of this study to test the hypothesis that there is a correlation between the oxaliplatin exposure (AUC in plasma) of patients to a microdose and exposure of patients to a treatment dose. If feasible, such an assay would consistently and accurately predict treatment dose exposure to oxaliplatin. Furthermore, that assessment of DNA adducts formed via the microdose would predict sensitivity and resistance to oxaliplatin-based therapy. Preliminary estimates of these parameters are secondary endpoints of this pilot study.

[figure not shown]

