8.2 Endpoint Definitions

8.2.1 Primary Endpoint

The primary endpoint is the feasibility of assessing therapeutic pharmacokinetic (PK) parameters of the therapeutic dose using the microdose in evaluable patients. For the purposes of this pilot study, this assessment will be considered feasible if the area under the curve extrapolated to infinity ($AUC_{0\rightarrow\infty}$) of the microdose and the therapeutic dose are within 2-fold of each other when normalized for differences in dose with a 95% confidence interval.

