8.2.1.1 Justification of the primary endpoint

Prior microdosing work suggests that a close relationship between multiple microdose and full dose pharmacokinetic parameters including $t_{1/2}$ and AUC can be observed [77]. In this study, we have chosen to focus on total exposure to treatment as total exposure is related to the primary dose limiting toxicity of oxaliplatin treatment (i.e. peripheral neuropathy) [81]. While a close relationship will be required for final development, a relationship within 2-fold will provide sufficient preliminary data to suggest that further development and optimization of the assay will be warranted.

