11.2 Analysis Plan

11.2.1 Primary Analyses

For the primary endpoint of feasibility is defined in **section 8.2.1**. We will correlate dose normalized $\text{AUC}_{0-\infty}$ parameters from phase 0 microdosing with parameters from the therapeutic dose of oxaliplatin for evaluable patients (the criteria for evaluation are listed in **section 8.1**). While assessment of PK feasibility is the primary endpoint of this study, we will use the totality of the data, including assessment of DNA adduct formation in PBMCs to determine the future development of this assay.

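### The only primary analysis named in 11.2.1 is a correlation, which cannot decide the 2-fold ratio criterion that 8.2.1 and 11.3 set

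*Combined protocol and SAP*

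**What the plan says.** Four sections of the combined protocol and SAP bear on the primary analysis.

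- **8.2.1 Primary Endpoint** sets a pass/fail rule. The assay is feasible if the AUCs to infinity of the microdose and the therapeutic dose are "within 2-fold of each other when normalized for differences in dose with a 95% confidence interval". Section 8.2.1.1 explains the margin: "a relationship within 2-fold will provide sufficient preliminary data" to justify developing the assay further.
- **11.3 Sample Size** turns that rule into a statistic. Six patients are to give "80% probability that a 95% CI for the ratio of geometric means of full dose and micro dose PK parameters is within 2 fold", with bounds of 0.5 and 2.
- **11.2.1 Primary Analyses** refers to 8.2.1 for the definition of feasibility. The analysis itself begins "We will correlate dose normalized" AUC and goes on "parameters from phase 0 microdosing with parameters from the therapeutic dose of oxaliplatin for evaluable patients". It names no ratio, log transformation or interval. It adds that all the data, DNA adducts included, will guide further development.
- **2.7 Rationale** gives "the primary aim of this study to test the hypothesis that there is a correlation between the oxaliplatin exposure (AUC in plasma") after a microdose and after a treatment dose.

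On variability, 11.3 says that the result depends on the CV of each parameter and on the within-person correlation. It gives a CV range of 0.3 to 0.5, taken from the half-lives of two other drugs, "which had good concordance between doses as well as adequate bioavailability". It states no correlation and no true ratio. Section 2.2 reports a mean AUC of 4.68 for oxaliplatin at 85 mg/m² and says "there was significant inter-patient variation in AUC (SD 1.40", in the same units).

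**The concern.** The endpoint and the sample size concern agreement: is the dose-normalized microdose AUC within a factor of two of the therapeutic one? The analysis section and the stated hypothesis concern association: do patients with a high microdose AUC also have a high therapeutic AUC? These are different questions. A microdose AUC that is consistently three times too high or too low can rank patients almost perfectly. One that agrees well on average can still give a modest r in six patients.

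The primary analysis as written therefore produces a number that does not answer the primary endpoint, and the number that would answer it appears only in the sample-size section. With six patients, the statistic that decides feasibility should be fixed before the data are seen.

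**Working it through.** **Inputs**

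- n = 6 pairs, bounds 0.5 to 2 (±ln 2 = ±0.693 on the log scale), 95% interval: 11.3.
- AUC CV = 1.40/4.68 = 0.299, about 0.30: 2.2. Taken as equal at both doses (assumption).
- CV range 0.3 to 0.5: 11.3.
- Within-person correlation rho on the log scale, and the true ratio: not given, so shown as ranges.

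**Step 1. Reproduce n = 6 for the ratio criterion.**

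Log SD of one AUC = sqrt(ln(1 + CV²)). For CV 0.30 this is 0.294.

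SD of the paired log ratio = log SD × sqrt(2(1 − rho)). For CV 0.30 and rho 0 this is 0.294 × 1.414 = 0.415.

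The criterion is met when |mean log ratio| + t × s/√6 < 0.693, with t(0.975, 5 df) = 2.571. Its probability is integrated over the chi-square distribution of s².

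| CV | rho | true ratio | P(95% CI within 0.5 to 2), n = 6 |
|---|---|---|---|
| 0.30 | 0 | 1 | 81% |
| 0.30 | 0.5 | 1 | 99% |
| 0.4 | 0 | 1 | 48% |
| 0.5 | 0 | 1 | 25% |
| 0.5 | 0.5 | 1 | 66% |
| 0.5 | about 0.61 | 1 | 80% |
| 0.30 | 0 | 1.25 | 60% |

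Six patients are thus reproduced at the lower end of the CV range even with rho 0. At the upper end they suffice only with rho of about 0.61 or more.

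**Step 2. Apply the correlation to the same data.**

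If one AUC is multiplied by k, its logarithm shifts by ln k. Pearson's r is computed from deviations about the mean, so the shift drops out. On the raw scale k cancels between numerator and denominator. The distribution of r therefore depends on rho and n only, not on the true ratio.

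For n = 6, rho 0.9 and CV 0.30:

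| true ratio | observed r, median (5th to 95th percentile) | P(95% CI within 0.5 to 2) |
|---|---|---|
| 1 | 0.92 (0.62 to 0.99) | about 100% |
| 3 | 0.92 (0.62 to 0.99) | 0% |

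For the second row, ln 3 = 1.099 lies well outside 0.693, while the SD of the log ratio is only 0.294 × sqrt(0.2) = 0.131.

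**Step 3. Illustration only: a test of the correlation.**

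The plan states no null value, alpha or threshold for r. Under an assumed two-sided 5% test of rho = 0, the critical value at n = 6 is |r| > 0.811. Power is then 17% at rho 0.5, 37% at 0.7, 56% at 0.8 and 82% at 0.9.

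**The case against.** The strongest reply is that the decision rule exists and that 11.2.1 adopts it. Its opening sentence sends the reader to 8.2.1, which says when the assay counts as feasible; 11.3 matches that rule, and no threshold for r appears anywhere. A reader might infer that an assay 3-fold off could be declared feasible on a high correlation. The documents do not support this, because the result would fail 8.2.1. That part of the reply stands. What remains is that 8.2.1 does not name the estimator or say which quantity carries the interval, and the section that should do so names a different statistic.

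A second reply is that the protocol uses the verb loosely. Endpoint 8.2.2.1 speaks of comparing parameters, and 11.2.2.1 carries this out by correlating them. That is fair, but the outputs listed there include a correlation coefficient and neither a ratio nor an interval, and 2.7 makes correlation the hypothesis itself.

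A third reply is that 2.7 is background and that the formal objective in 1.1.1 is feasibility. This stands, and it limits the weight of the wording in 2.7.

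**Conclusion.** The point holds as a mismatch between the named analysis and the endpoint. The wording of 11.2.1 and 2.7 is at fault; 8.2.1 and 11.3 agree with each other. The main argument needs no assumed test, because r behaves identically at a true ratio of 1 and of 3 while the interval criterion moves from about 100% to 0% (rho 0.9, CV 0.30, equal variability at both doses, log-normal AUCs).

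Three stronger readings go beyond the documents.

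- *Six patients are too few because a correlation needs rho of about 0.90 for 80% power.* The plan specifies no such test. The required rho runs from 0.85 to 0.92 depending on the test chosen.
- *Agreement within 2-fold would usually come with a non-significant correlation.* Under the illustrative test this is true only below rho of about 0.77, and the documents give no rho.
- *Six patients are secure for the ratio criterion.* The 80% is conditional. At a true ratio of 1, and over the CV range in 11.3, it can fall to 25% (CV 0.5, rho 0). At CV 0.30 and rho 0, a true ratio of 1.25 gives 60%.

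The consequence is limited, because this is a pilot and 11.2.1 bases further development on all the data. It is still worth correcting before analysis.

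**What to change.** **11.2.1.** Replace the sentence on correlating the AUCs with: *The primary analysis is the geometric mean of the within-patient ratio of dose-normalized AUC to infinity (phase 0 microdose / therapeutic dose), estimated from the mean of the paired log differences with a two-sided 95% t interval and back-transformed. Feasibility is met if the interval lies within 0.5 to 2 (8.2.1, 11.3). Individual ratios are listed. The correlation is reported with its 95% CI as description only and does not decide feasibility.* The bounds are reciprocal, so the direction of the ratio does not affect the decision.

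**2.7.** Restate the primary aim as agreement within 2-fold.

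**11.3 (minor).** Leave n unchanged. State the assumed AUC CV, within-person correlation and true ratio, and show that the 80% is conditional on them, as in the first table above. If the CV comes from 2.2, note that 2.2 does not say which platinum fraction was measured or whether its AUC was extrapolated to infinity.

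**Cost.** One passage in 11.2.1, one sentence in 2.7 and a short addition to 11.3. There are no added patients, samples or visits.
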